8. SAFETY

8.1. Adverse Events

Any Adverse Events or Serious Adverse Events (defined below) encountered in the study will be monitored and reported to the BUMC IRB as per established procedures.

Adverse Event: Any untoward or unfavorable physical or psychological occurrence in a human participant, including any abnormal sign (for example, abnormal physical exam or laboratory finding), symptom, or disease temporally associated with the participant's participation in the research, whether or not considered related to the participant's participation in the research.

Serious Adverse Event: Any adverse event that:

- 1) Results in death
- 2) Is life-threatening (places the participant at immediate risk of death from the event as it occurred)
- 3) Results in inpatient hospitalization or prolongation of existing hospitalization
- 4) Results in a persistent or significant disability/incapacity
- 5) Based upon appropriate medical judgment, may jeopardize the participant's health and may require medical or surgical intervention to prevent one of the other outcomes listed in this definition.

Unanticipated Problem is defined as an event, experience or outcome that meets **all three** of the following criteria:

- is unexpected; AND
- is related or possibly related to participation in the research; AND
- suggests that the research places participants or others at a greater risk of harm (including physical, psychological, economic, or social harm) than was previously known or recognized.

Possibly related means there is a reasonable possibility that the incident, experience, or outcome may have been caused by the procedures involved in the research

Unexpected means the nature, severity, or frequency of the event is not consistent with either:

- the known or foreseeable risk of adverse events associated with the procedures involved in the research that are described in (a) the protocol-related documents, such as the IRB-approved research protocol, any applicable investigator brochure, and the current IRB-approved informed consent document, and (b) other relevant sources of information, such as product labeling and package inserts; or
- the expected natural progression of any underlying disease, disorder, or condition of the participant(s) experiencing the adverse event and the participant's predisposing risk factor profile for the adverse event.

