conducted to assess frequency of events, severity, seriousness, and relatedness to determine any potential trending study related items that may indicate a potential safety concern.

The data for adverse events (observed by study staff or spontaneously reported by caregivers) will be aggregated using descriptive statistics. Overlap of adverse events will be recorded.

Caregiver reported treatment-related adverse events will be recorded using MedDRA Version 24.1.

Severity of adverse events will be categorized as follows: Mild-Symptom(s) barely noticeable with no reported participant discomfort; Moderate- Symptom(s) reported as uncomfortable; Severe- Symptom(s) causing severe discomfort resulting in participant withdrawal. Relatedness of reported events will be categorized as follows: Unrelated- The event deemed to be clearly not study related; Possibly related- The event is temporally aligned with study activities but possibly may be due to another circumstance; Related- The event is temporally aligned to study activities with no alternative causes present.

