8.3 Reporting Plans

The Principal Investigator at BMC/BU Medical Campus will report Unanticipated Problems, safety monitors' reports, and Adverse Events to the BMC/BU Medical Center IRB in accordance with IRB policies:

- Unanticipated Problems occurring at BMC/BU Medical Campus will be reported to the IRB within 7 days of the investigator learning of the event.
- Adverse Events (including Serious Adverse Events) will be reported in summary at the time of continuing review, along with a statement that the pattern of adverse events, in total, does not suggest that the research places participants or others at a greater risk of harm than was previously known.
- Monthly reviews of blinded unanticipated problems and adverse events will be reviewed with Pfizer to assess frequency of events, severity, seriousness, and relatedness to determine any potential trending study related items that may indicate a potential safety concern.

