8.4 Research Related Injury

Possible social risks: These are extremely low in this study and pertain to the unintentional release of personal information.

Mitigation of social risks: To safeguard confidentiality and the privacy of protected information, each study participant will be assigned a unique code number. A separate file linking the participants' name with study number and identifiers will be kept in a password-protected data file, accessible only by the PI and the study coordinator. All study forms will be kept in secure locked file cabinets. The study investigators will assume full responsibility to maintain the confidentiality of all data. All study results will be presented only as statistical aggregates that will neither identify, nor permit identification of, individual participants.

Possible risk associated with digital health devices: The risks associated with these devices include physical discomfort if the participant is not used to wearing wrist accelerometers and/or ankle devices, and possible skin irritation or reaction, such as an AD flare-up in children with the skin condition. If the participant experiences skin irritation or notice signs of an AD flare-up in the area that the child wears the device(s), they will be instructed to remove the device(s) and notify the study team immediately.

Mitigation of risks associated with digital health devices: If the participant is unable to wear the device due to discomfort (or AD flare up) the participant will notify study staff and the Principal Investigator may allow the participant to continue the study without wearing the discomforting device or withdraw the

participant from the study. Devices will be optional for child participants who have active AD on location of device placement, with a minimum of at least one wrist device needed for enrollment.

Possible risk associated with tape stripping: Tape stripping is routinely performed and is considered a minimally invasive approach for identifying biomarkers for Atopic Dermatitis and is an acceptable alternative to traditional biopsies. The only minimal risk associated with tape stripping is mild discomfort and potentially superficial surface reddening of the skin at the location of the tape. This is typically reported after 50-60 tape stripplings. In this study we will only be doing ~20 tape stripplings per sample. Tape stripping sensation is similar to removal of a band-aid.

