Mitigation of risk associated with tape stripping: Tape stripplings will only be conducted three times with a minimum of 3 days between each tape stripping. If the participant experiences discomfort, adjacent sites to previous stripping area will be used.

Possible risk associated with crisaborole: Possible risks associated with crisaborole include application site pain or burning/stinging sensation (lasting one to two days) and/or hypersensitivity reaction and/or development of a skin allergy and/or severe pruritis and/or swelling and/or erythema. Less common risks (<1%) include contact urticaria (hives - a skin reaction that results in red, itchy welts). AD by nature is a disease that has recurrent flares on active treatment or without active treatment. Therefore, participants on crisaborole or vehicle could experience worsening of their natural course of disease.

Mitigation of risk associated with crisaborole: If the participant develops a hypersensitivity reaction, severe pruritis, swelling, or erythema, (and/or development of skin allergy (e.g. hives)), dosing will be discontinued and the site will be contacted, and the participant should seek medical attention as needed. If minor application site pain or burning/stinging sensation is reported, and participant is uncomfortable with continuation, the principal investigator may allow the participant to continue in the study with dosing discontinued, or participant will be withdrawn. If signs and symptoms of hypersensitivity occur, discontinue EUCRISA immediately and initiate appropriate therapy. **Hypersensitivity Reactions** Advise patients to discontinue EUCRISA and seek medical attention immediately if signs or symptoms of hypersensitivity occur [see *Warnings and Precautions (5.1) from label*]. **Administration Instructions** Advise patients or caregivers that EUCRISA is for external use only and is not for ophthalmic, oral, or intravaginal use. All participants may withdraw from the study at any time, including if they experience worsening of symptoms.

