Possible Risk Associated with vehicle treatment: Possible risks associated with vehicle include application site pain or burning/stinging sensation, severe pruritis (itching), swelling, redness and/or hypersensitivity reaction (an exaggerated immune response which may cause skin discomfort) and/or development of a skin allergy. Possible risks associated with vehicle treatment where vehicle contains the excipients of crisaborole ointment, and the base of crisaborole ointment has no difference in appearance, texture, color, or odor to crisaborole ointment, 2% and as such no specific risks identified other than hypersensitivity reaction and/or development of skin allergy. No additional risks are known with respect to vehicle treatment as it provides white petrolatum as the main excipient and base of crisaborole ointment, 2%, which was selected for its emollient properties and favorable tolerability profile, where the importance of an emollient effect is highlighted by the use of emollients in basic skin care for patients with AD, to aid in restoration of barrier function

Mitigation of Risk Associated with vehicle treatment: If the participant develops a hypersensitivity reaction, severe pruritis (itching), swelling, redness (and/or development of skin allergy (e.g. hives)), dosing will be discontinued and the site will be contacted, and the participant should seek medical attention as needed. If minor application site pain or burning/stinging sensation is reported, and participant is uncomfortable with continuation, the principal investigator may allow the participant to continue in the study with dosing discontinued, or participant will be withdrawn. AD by nature is a

disease that has recurrent flares on active treatment or without active treatment. Therefore, participants on vehicle could experience worsening of their natural course of disease.

Participants may become bored/fatigued over the course of a testing session. The same considerations apply to the study visits.

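### The severe adverse event grade requires withdrawal from the study, so severe discomfort in a participant who stays can be graded no higher than moderate

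*Combined protocol and SAP*

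**What the plan says.** Section 8.2 (Safety Review) sets out three severity grades:

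- "Mild-Symptom(s) barely noticeable with no reported participant discomfort"
- "Moderate- Symptom(s) reported as uncomfortable"
- "Severe- Symptom(s) causing severe discomfort resulting in participant withdrawal"

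Section 8.3 (Reporting Plans) has blinded events reviewed monthly with the sponsor "to assess frequency of events, severity, seriousness, and relatedness". Section 8.2 describes the same monthly review and says that adverse events will be summarised descriptively. Section 9 lists a summary of adverse events among the planned analyses.

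Section 8.4 (Research Related Injury) covers what happens after a reaction:

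- **Device discomfort:** "the Principal Investigator may allow the participant to continue the study without wearing the discomforting device", or may withdraw the participant.
- **More serious ointment reactions:** "If the participant develops a hypersensitivity reaction, severe pruritis, swelling, or erythema, (and/or development of skin allergy (e.g. hives)), dosing will be discontinued". The site is then contacted and medical attention sought as needed. Study withdrawal is not mentioned. The vehicle paragraph has a parallel clause.
- **Minor application site pain, burning or stinging:** where the participant is uncomfortable going on, "the principal investigator may allow the participant to continue in the study with dosing discontinued, or participant will be withdrawn".

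Section 8.1 (Adverse Events) uses severity in one further place: "Unexpected means the nature, severity, or frequency of the event is not consistent with either" the known risks or the expected course of the disease.

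**The concern.** The scale mixes two things: how intense the symptom was, and whether the participant left the study. A grade built this way cannot be read as intensity. The same symptom, felt equally strongly, is severe in a child whose family withdraws and moderate in a child whose family continues.

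Severity is one of four attributes that the monthly reviews examine for a possible safety signal, and those reviews would see too few severe events. Events would still be recorded and reviewed for frequency, seriousness and relatedness, so the loss is confined to the severity information. The grade might also bear on whether an event is judged unexpected under Section 8.1. The documents do not say that the Section 8.2 grade is used for that judgement, but they define no other.

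**Working it through.** The point is about a definition, so the main check sets the provisions side by side. There is no figure in the plan to reproduce.

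**Step 1: apply the grades to severe discomfort without withdrawal.**

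| Grade | Condition in Section 8.2 | Met? |
|---|---|---|
| Mild | Barely noticeable and no discomfort reported | No |
| Moderate | Discomfort reported | Yes |
| Severe | Severe discomfort and resulting withdrawal | No, the second part fails |

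Moderate is the only grade that fits.

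**Step 2: look for another route to the severe grade.** There is none. The criteria in Section 8.1 define seriousness, which Section 8.3 lists separately from severity. MedDRA is named only as the terminology for recording events.

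**Step 3: ask whether the case can arise.**

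- Section 8.4 stops dosing for hypersensitivity, severe itching, swelling or redness and does not mention withdrawal. An event that the protocol itself calls severe could be graded moderate.
- The protocol treats stopping dosing and leaving the study as different acts. For body surface area above 40%, Section 8.2 states both. For minor application site pain, Section 8.4 offers them as alternatives. That clause covers only minor symptoms, so it shows the distinction but is not an example of a severe case.
- The device clause in Section 8.4 sets no limit on intensity, so the grade can depend on the investigator's decision about continuation.
- Treatment lasts two weeks and ends at the Day 15 visit. A severe event close to that visit leaves little to withdraw from.

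**Step 4: effect on the counts.** Let S be the number in an arm with severe discomfort and w the share who withdraw because of it.

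- Recorded severe = S × w
- Undercount = S × (1 − w), which is never negative
- Recorded ratio between arms (A to B) = true ratio × (w in arm A ÷ w in arm B)

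The documents give neither S nor w. As an assumed illustration, take true counts of 8 in arm A and 4 in arm B: ratio 2, difference 4, total 12. For scale, 270 ÷ 2 = 135 children are expected per arm; that number does not enter the calculation.

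| w in A | w in B | Recorded A | Recorded B | Ratio | Difference | Total |
|---|---|---|---|---|---|---|
| 0.50 | 0.50 | 8 × 0.50 = 4 | 4 × 0.50 = 2 | 2 | 2 | 6 |
| 0.25 | 0.75 | 8 × 0.25 = 2 | 4 × 0.75 = 3 | 0.67 | −1 | 5 |
| 0.75 | 0.25 | 8 × 0.75 = 6 | 4 × 0.25 = 1 | 6 | 5 | 7 |

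The total matters for the blinded monthly reviews: 12 severe cases appear as 5 to 7. With equal shares the ratio is preserved but the difference is halved. With unequal shares the contrast can be reversed or exaggerated.

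**The case against.** The strongest counter-argument is that the definition may describe what follows from severe discomfort, namely withdrawal. The stopping provision at the end of Section 5 says that no procedure goes on once a participant expresses discomfort. If every participant with severe discomfort leaves, w = 1 and nothing is missed. On that reading, deleting the withdrawal clause could also remove a withdrawal rule.

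This does not hold. The sentence is introduced as a way of categorising severity, not as a rule for withdrawing anyone. The Section 5 provision stops the procedure, not participation. Section 8.4 says that participants may withdraw if symptoms worsen, which leaves the choice to them.

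Other points stand in part:

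- **Existing capture.** The Day 15 or early termination visit already records disposition and reasons for leaving. Dosing is tracked by record sheets and tube weights, and staff assess irritation and discomfort at each visit. This makes the fix easier, but none of it gives a severe grade to someone who stays.
- **Thin examples.** No provision says outright that a participant with a severe event remains in the study. For the severe reactions the argument rests on Section 8.4 stopping dosing and being silent on withdrawal.
- **Contrast between arms.** The plan specifies no comparison of severity by arm, and the documents give no reason to expect shares as different as 0.25 and 0.75. The reversal shows what is possible, not what is likely.
- **Expectedness.** The link to Section 8.1 is an inference from the absence of another scale.

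**Conclusion.** The concern holds. As written, Section 8.2 grades severe discomfort without withdrawal as moderate, and Section 8.4 leaves room for such cases. This conclusion follows from the wording alone and needs no assumed number.

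Within an arm the error runs one way: severe counts can be understated but not overstated. Its size cannot be derived from the documents, and the figures above rest entirely on assumed values of S and w. A descriptive contrast between arms would be distorted in either direction only if such a contrast were made; its ratio would shift only if withdrawal shares differed.

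The defect should be corrected, but its reach is limited. Serious events are defined independently, all events are still recorded, and no efficacy estimate, test or sample size changes. What is lost is the ability to read the severity summary as a measure of intensity.

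**What to change.** In Section 8.2, define the severe grade by symptom intensity alone and drop the withdrawal condition. Add a field to the adverse event form for the action taken: dosing continued, dosing stopped, device removed, or participant withdrawn. It can build on the disposition record at the final visit. Summarise severity and action taken descriptively by arm in the final report, and keep the monthly reviews blinded.

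Reconcile the Section 8.2 grades with the continuation and discontinuation provisions in Section 8.4. The change should state that it affects only how events are graded and recorded; the rules on stopping dosing and on withdrawal stay as they are.

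The cost is one sentence of protocol wording, one form field and slightly more data entry. The reported number of severe events may rise. If enrolment has begun, events already graded moderate need checking against the new wording.

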8.3 Reporting Plans

The Principal Investigator at BMC/BU Medical Campus will report Unanticipated Problems, safety monitors' reports, and Adverse Events to the BMC/BU Medical Center IRB in accordance with IRB policies:

- Unanticipated Problems occurring at BMC/BU Medical Campus will be reported to the IRB within 7 days of the investigator learning of the event.
- Adverse Events (including Serious Adverse Events) will be reported in summary at the time of continuing review, along with a statement that the pattern of adverse events, in total, does not suggest that the research places participants or others at a greater risk of harm than was previously known.
- Monthly reviews of blinded unanticipated problems and adverse events will be reviewed with Pfizer to assess frequency of events, severity, seriousness, and relatedness to determine any potential trending study related items that may indicate a potential safety concern.

8.4 Research Related Injury

Possible social risks: These are extremely low in this study and pertain to the unintentional release of personal information.

Mitigation of social risks: To safeguard confidentiality and the privacy of protected information, each study participant will be assigned a unique code number. A separate file linking the participants' name with study number and identifiers will be kept in a password-protected data file, accessible only by the PI and the study coordinator. All study forms will be kept in secure locked file cabinets. The study investigators will assume full responsibility to maintain the confidentiality of all data. All study results will be presented only as statistical aggregates that will neither identify, nor permit identification of, individual participants.

Possible risk associated with digital health devices: The risks associated with these devices include physical discomfort if the participant is not used to wearing wrist accelerometers and/or ankle devices, and possible skin irritation or reaction, such as an AD flare-up in children with the skin condition. If the participant experiences skin irritation or notice signs of an AD flare-up in the area that the child wears the device(s), they will be instructed to remove the device(s) and notify the study team immediately.

Mitigation of risks associated with digital health devices: If the participant is unable to wear the device due to discomfort (or AD flare up) the participant will notify study staff and the Principal Investigator may allow the participant to continue the study without wearing the discomforting device or withdraw the

participant from the study. Devices will be optional for child participants who have active AD on location of device placement, with a minimum of at least one wrist device needed for enrollment.

Possible risk associated with tape stripping: Tape stripping is routinely performed and is considered a minimally invasive approach for identifying biomarkers for Atopic Dermatitis and is an acceptable alternative to traditional biopsies. The only minimal risk associated with tape stripping is mild discomfort and potentially superficial surface reddening of the skin at the location of the tape. This is typically reported after 50-60 tape stripplings. In this study we will only be doing ~20 tape stripplings per sample. Tape stripping sensation is similar to removal of a band-aid.

Mitigation of risk associated with tape stripping: Tape stripplings will only be conducted three times with a minimum of 3 days between each tape stripping. If the participant experiences discomfort, adjacent sites to previous stripping area will be used.

Possible risk associated with crisaborole: Possible risks associated with crisaborole include application site pain or burning/stinging sensation (lasting one to two days) and/or hypersensitivity reaction and/or development of a skin allergy and/or severe pruritis and/or swelling and/or erythema. Less common risks (<1%) include contact urticaria (hives - a skin reaction that results in red, itchy welts). AD by nature is a disease that has recurrent flares on active treatment or without active treatment. Therefore, participants on crisaborole or vehicle could experience worsening of their natural course of disease.

Mitigation of risk associated with crisaborole: If the participant develops a hypersensitivity reaction, severe pruritis, swelling, or erythema, (and/or development of skin allergy (e.g. hives)), dosing will be discontinued and the site will be contacted, and the participant should seek medical attention as needed. If minor application site pain or burning/stinging sensation is reported, and participant is uncomfortable with continuation, the principal investigator may allow the participant to continue in the study with dosing discontinued, or participant will be withdrawn. If signs and symptoms of hypersensitivity occur, discontinue EUCRISA immediately and initiate appropriate therapy. **Hypersensitivity Reactions** Advise patients to discontinue EUCRISA and seek medical attention immediately if signs or symptoms of hypersensitivity occur [see *Warnings and Precautions (5.1) from label*]. **Administration Instructions** Advise patients or caregivers that EUCRISA is for external use only and is not for ophthalmic, oral, or intravaginal use. All participants may withdraw from the study at any time, including if they experience worsening of symptoms.

Possible Risk Associated with vehicle treatment: Possible risks associated with vehicle include application site pain or burning/stinging sensation, severe pruritis (itching), swelling, redness and/or hypersensitivity reaction (an exaggerated immune response which may cause skin discomfort) and/or development of a skin allergy. Possible risks associated with vehicle treatment where vehicle contains the excipients of crisaborole ointment, and the base of crisaborole ointment has no difference in appearance, texture, color, or odor to crisaborole ointment, 2% and as such no specific risks identified other than hypersensitivity reaction and/or development of skin allergy. No additional risks are known with respect to vehicle treatment as it provides white petrolatum as the main excipient and base of crisaborole ointment, 2%, which was selected for its emollient properties and favorable tolerability profile, where the importance of an emollient effect is highlighted by the use of emollients in basic skin care for patients with AD, to aid in restoration of barrier function

Mitigation of Risk Associated with vehicle treatment: If the participant develops a hypersensitivity reaction, severe pruritis (itching), swelling, redness (and/or development of skin allergy (e.g. hives)), dosing will be discontinued and the site will be contacted, and the participant should seek medical attention as needed. If minor application site pain or burning/stinging sensation is reported, and participant is uncomfortable with continuation, the principal investigator may allow the participant to continue in the study with dosing discontinued, or participant will be withdrawn. AD by nature is a

disease that has recurrent flares on active treatment or without active treatment. Therefore, participants on vehicle could experience worsening of their natural course of disease.

Participants may become bored/fatigued over the course of a testing session. The same considerations apply to the study visits.

